6.1.2 CO OR PLACEBO CYLINDERS

The gas cylinders for this clinical trial are AG or A3 aluminum cylinders with a CGA 500 valve and will be supplied by Praxair Healthcare Services (Morrisville, PA). The cylinder contains approximately 360 liters of 5000 ppm (0.5%) CO in room air (21% oxygen) and poses no increased flammability risk. Placebo tanks will contain medical grade air in identical appearing cylinders. The gas cylinder's nominal size is 5 inches in diameter by 17 inches tall. Given the flow limitation from the regulator of ~7 liters per minute and a minimum of 6 air exchanges per hour in an average 15x15x10 ICU room, we do not expect ambient CO levels to exceed the OSHA permissible exposure limit (PEL) of 50 ppm as an 8 hour time-weighted average. We measured ambient CO levels during our animal studies using the COventDS and were unable to detect increases in ambient CO levels throughout assembly, calibration, and delivery of CO to the animals. In addition, we simulated CO administration with an ICU ventilator (Puritan-Bennett 840), CO Delivery System, and lung model in an ICU room at Massachusetts General Hospital at 500 ppm for over 2 hours and ambient CO levels were near zero and well below the OSHA PEL.

6.1.3 DOSING AND ADMINISTRATION

Inhaled CO or placebo air will be administered to participants via the COventDS, which will be calibrated and connected to the ventilator (**Figure 9**). Ventilator management will follow the ARDS Network lower tidal volume (6 mL/kg PBW) protocol¹³. Subjects randomized to CO will be administered iCO at 200 ppm for 20 min as a “test dose” on each treatment day to determine in real-time each subject’s CFK equation-determined personalized dose.

COHb levels will be measured before and after the 20 min test dose, and these two levels entered into the CFK equation calculator program to estimate DL_{CO} and compute the iCO dose to achieve a COHb level of 7% (target 6-8%) at 90 min. After the iCO dose is determined, subjects will be administered iCO at the CFK equation-determined personalized dose (200-500 ppm) but **not to exceed 500 ppm or 90 min total (including test dose)**. Subjects randomized to placebo will be administered medical grade air.

The study drug will be administered for up to 90 minutes daily for three days following randomization or until discontinuation of mechanical ventilation, whichever occurs first. For patients who have a tracheostomy, the equivalent of extubation for the purposes of this protocol will be breathing via tracheostomy with unassisted breathing.

The study drug concentration will be monitored continuously with the COventDS built-in analyzer and blood will be drawn at serial time points for arterial blood gas (ABG) analysis and safety monitoring of COHb levels as described in **Section 6.1.4**.

6.1.4 CO MONITORING

The study drug concentration will be monitored continuously with the COventDS built-in analyzer to assure that the accurate dose is delivered. A physician investigator will assess subjects prior to daily iCO treatment. Subjects will have blood drawn daily for measurement of COHb and lactate prior to study drug administration. If COHb $\geq 3\%$ (assessed by unblinded physician) or lactate ≥ 4 mmol/L, the study drug will be held and the subject will be reassessed for treatment the following day. An electrocardiogram (EKG) will also be performed daily prior to study drug administration to evaluate for cardiac exclusion criteria. Blood COHb levels will be measured with an IL GEM Premier Co-oximeter and SpCO measured with a noninvasive pulse oximeter (Masimo Radical-7).

All CO monitoring will be carried out by the administering RT and physician study staff member OR physician study staff member alone and concealed from the study coordinator and clinical team. The physician study staff member will be responsible for maintaining a separate password-protected limited-access project within the database with the subject identification number and CO-related measurements (SpCO, COHb, ambient CO) which the study coordinator will not have access to.

Blood for COHb Monitoring

Blood (arterial or venous) will also be drawn at 20, 40, 60, 75, 90, and 180 minutes for safety monitoring of COHb levels. If an arterial line is not available, venous blood will be used for COHb monitoring as we³⁸ and others¹³⁷⁻¹³⁹ have shown that venous levels are as accurate and reliable as arterial measurements. Blood (arterial or venous) will also be drawn for blood gas analysis (using the IL GEM Premier Co-oximeter or local clinical lab) at 90 minutes or at the completion of treatment, if discontinued sooner than 90 minutes. If arterial blood is not available and venous blood gas is used, PaO_2/FiO_2 will be estimated using the formula $SpO_2/FiO_2 = 64 + 0.84 \times PaO_2/FiO_2$, as long as $SpO_2 \leq 97\%$ and subject remains intubated as described in the Statistical Analysis Plan.

The unblinded physician will review and adjudicate COHb measurements and communicate any study drug treatment holds to the administering study staff. COHb levels will be entered into the electronic case report forms (eCRFs) in a separate limited-access project in StudyTRAX by the unblinded RT or physician. The study drug will be administered for up to 90 minutes daily for up to 3 days following randomization or until discontinuation of mechanical ventilation, whichever occurs first.

COVentDS CO Monitoring

The concentration of the study drug will be measured by the built-in gas monitor in the COVentDS. The CO Delivery System contains an inhaled gas monitor, which is an electrochemical device that monitors the inhaled gas for concentrations of CO (0-800 ppm) and O₂ (15-100%) to assure that safe levels are inhaled. The sample pump maintains a constant flow of gas to the sensors. Samples of inspired gases are taken with a continuous ~400 mL/min sample pump just proximal to the patient's airway to reflect actual inspired gases. Alarms will sound on high or low CO or O₂ concentrations.

Ambient Air Monitoring

Ambient air CO concentrations will be measured in real time with a Dräger Pac 7000 CO detector to assure that ambient levels are maintained within the recommended limits for occupational exposure of a maximum of 50 ppm. Ambient air CO detectors will be calibrated every 6 months per the manufacturer's instructions to ensure proper functioning.

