More recently, we completed a Phase I trial of low fixed-dose iCO in patients with sepsis-induced ARDS^{111,112}. Twelve participants were randomized to iCO or placebo air 2:1 in two cohorts. Four subjects each were administered iCO (100 ppm in Cohort 1 or 200 ppm in Cohort 2) or placebo for 90 minutes for up to 5 consecutive days. CO treatment was well tolerated and no participants exceeded a COHb level of 10%. There were no administration-associated AEs or study-related serious AEs (SAEs). Baseline COHb levels were not different across treatment groups. CO-treated participants had a significant increase in COHb ($3.48 \pm 0.7\%$ [Cohort 1]; $4.9 \pm 0.28\%$ [Cohort 2]) compared with placebo-treated subjects ($1.97 \pm 0.39\%$), which did not differ from baseline levels (Figure 2). The maximum COHb

(Figure 2). The maximum COHb

level in Cohort 1 was 4.4% and 6.87% in Cohort 2. The maximum change in COHb from baseline to 90 minutes (Δ 90 min COHb) was 2.5% in Cohort 1 and 4% in Cohort 2. There was no significant increase in COHb in placebo subjects.

Taken together, these findings demonstrate that experimental administration of several different concentrations of CO is well tolerated and that low dose iCO can be safely administered to subjects in a controlled research environment.

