6.3 MEASURES TO MINIMIZE BIAS: RANDOMIZATION AND BLINDING

Eligible participants will be randomized to one of the two treatment arms using a permuted block method¹⁴⁶ with random block sizes. The randomization ratio will be 2:1 iCO:placebo. The randomization will not be stratified by any factors. The study biostatistician will verify all the necessary randomization information (blinding method, randomization method, block size, and number of treatment groups) in the StudyTRAX randomization configuration module.

Site investigators will review all potential study participants with one of the CCC physician members. Following informed consent, the unblinded administering RT or physician or blinded study coordinator will randomize subjects in the database using the StudyTRAX randomization tool. The unblinded administering RT or physician will obtain the subject's treatment assignment through the "View Treatment" button in the blinded database, a privilege granted to unblinded RTs and physicians only. CO-related measurements (SpCO, COHb, ambient CO) and drug-related information will be in a separate project within the database, which the blinded study coordinators will not have access to. Permission to this limited-access project will only be granted to unblinded study personnel by the PI, as it contains treatment-specific information such as CO monitoring and study drug administration data.

The study drug assignment will be blinded to the subject, clinical team, study coordinators, and other study staff with the exception of the administering study staff (RT and physician OR physician alone), who will be unblinded to the treatment assignment to ensure subject safety. We chose this partially double-blind design to ensure safe iCO administration and an unblinded assessment of COHb levels in order not to exceed potentially toxic thresholds.

To maintain blinding, the placebo air cylinders are identical in appearance as the CO cylinders (with the exception of different CGA valves required by the manufacturer Praxair). Cylinders will also be shrouded in dark sleeves to ensure blinding. The placebo air will be administered via inhalation via the COventDS

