and delivered to subjects in an identical fashion as those randomized to CO. To ensure that the subject, study coordinator, and clinical staff remain blinded to the study drug assignment, the administering RT and physician study staff member OR physician study staff member alone will conceal the gas cylinders, CO delivery device, and measurements of COHb, SpCO, and ambient CO levels. Unblinded test results will be kept in a separate location from the blinded test results and concealed from the study coordinators.

The unblinded administering physician will be responsible for maintaining a separate password-protected limited-access project within the database with the subject identification number and CO-related measurements (SpCO, COHb, ambient CO) which the study coordinator will not have access to. While the administering investigator will be unblinded throughout the study due to safety monitoring, they will only be unblinded to the treatment assignment for subjects enrolled at their own site. Investigators will otherwise be blinded to the study treatment assignment for subjects enrolled at the other sites. The lead RT ([name]) may become unblinded to the treatment assignments at other sites to assist with study drug administration procedures if necessary.

If the clinical team believes that unblinding is medically necessary in order to properly treat the patient, the unblinded administering physician can disclose study product assignment. If there is time to do so, the unblinded administering physician should discuss this unblinding with the unblinded CCC physician prior to the disclosure. All episodes of unblinding, whether deliberate or inadvertent, will be reported to the DSMB at the next routine report.

A blinded study physician at each site will review all AEs and will assess their relationship to the study intervention. Additional AE adjudication will be provided by one of the Medical Monitors ([name] or [name]). In addition to blinded adjudication of AEs, investigators blinded to treatment allocation will assess chest X-rays required for the calculation of the LIS score. De-identified chest X rays at each site will be reviewed centrally by blinded investigators at BWH.

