8.1.1 STUDY SAMPLE COLLECTION

Sample collection will be done according to the **Schedule of Activities (SoA)** in **Section 1.3**.

COHb Levels: COHb levels will be measured using the IL GEM Premier Co-oximeter at specified time points on Days 1 through 3. See **Section 8.5.3**.

Plasma Samples: Blood (4 mL) will be collected pre-treatment and post-treatment (90 mins and 3 hrs) on days 1-3 in EDTA anti-coagulated tubes for plasma isolation and measurement of biomarkers of mitochondrial dysfunction, inflammasome activation, lipid mediators, and cytokines. Blood (4 mL) will also be collected for plasma isolation on Day 5. Plasma will be obtained and divided immediately after centrifugation into equal aliquots in specified tubes and frozen at -80°C.

RNA Samples: Blood (2.5 mL) will be collected pre-treatment and post-treatment (90 min and 3 hrs) on days 1-3 in Paxgene tubes for RNA isolation, and frozen at -80°C. Blood (2.5 mL) will also be collected in Paxgene tubes for RNA isolation on Day 5 and frozen at -80°C.

DNA Samples: Cell pellets will be obtained for future DNA isolation from the blood collected in EDTA tubes on days 1-3 and on day 5. Cell pellets will be isolated pre-treatment and post-treatment (at 90 min and 3 hrs) on days 1-3.

Primary Cell Isolation: An additional 8 mL of blood will be drawn for isolation of peripheral blood mononuclear cells (PBMCs) pre-treatment on day 1 and post-treatment on day 3. This tube may be used to isolate cell pellets (for future DNA isolation) if unable to obtain an adequate pellet from the 4 mL tube on days 1 and 5.

Urine Sample Collection: Between 50-100 mL of urine will be collected in a sterile specimen container on days 1-3 and on Day 5. Cell pellets will be isolated pre-treatment and post-treatment (at 90 min and 3 hours) to obtain RNA and protein, as well as mtDNA.

Discarded Specimens: Discarded bronchoalveolar lavage (BAL) fluid and plasma will be obtained (when available) for levels of cytokines, mediators/biomarkers, and protein. Plasma and BAL fluid will be divided into equal aliquots in specified tubes and frozen at -80°C.

A total of approximately 90 mL of blood will be collected for research samples during the study from each study subject as follows:

| Sample collection | Day 1 | Day 2 | Day 3 | Day 5 | Total Volume |
|---|----------------|----------------|----------------|----------------|--------------|
| ABG, lactate, and COHb analysis | 3 mL | 3 mL | 3 mL | | 9 mL |

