8.5.2 PRE-TREATMENT ASSESSMENTS (DAY 1 – 3)

The following assessments will be done on Days 1-3 prior to study drug administration. **No treatment will be started before these assessments are performed and the pre-treatment administration checklist is completed by the study investigator.**

- **Blood Gas Analysis (arterial or venous):** Arterial or venous blood will be drawn for blood gas analysis using the IL GEM Premier Co-oximeter or local laboratory at each center. The blood gas will be assessed daily prior to starting study drug administration. The study drug will not be started until this result is obtained and reviewed by the study physician investigator for a potential study hold. The following values will be recorded from the ABG or VBG results: pH, PCO₂, PO₂, and base excess or deficit.
- **Hemoglobin Level:** Hemoglobin will be measured and assessed daily prior to study drug administration. The hemoglobin level will be measured by the local laboratory at each center. The study drug will not be started until this result is obtained and reviewed by the study physician investigator for a potential study hold.
- **COHb Level:** The baseline COHb level will be drawn and assessed by an unblinded physician investigator, just prior (less than 15 minutes) to starting the study drug administration. COHb will be measured by study investigators using an IL GEM Premier Co-oximeter at the subject's bedside. These results are obtained within less than 5 minutes. The study drug will not be started until this result is obtained and reviewed for a potential study hold. All COHb level result printouts should be filed in the unblinded subject file.
- **Lactate Level:** Lactate level will be measured and assessed daily by the local laboratory at each center prior to study drug administration. The study drug will not be started until this result is obtained and reviewed by the study physician investigator for a potential study hold.
- **EKG:** A 12 lead EKG will be obtained and reviewed daily by the study staff physician prior to study drug administration to evaluate for cardiac exclusion criteria (acute MI, ACS, or unstable atrial or ventricular arrhythmia). The study drug will not be started until the EKG is obtained and reviewed by the study physician investigator for a potential study hold. The EKG will also be officially read locally at each site.

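### Section 6.1.4 lets the 90-minute study blood gas, drawn at the intended COHb peak, be run in the local clinical laboratory, outside the protocol's arrangements for concealing COHb

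*Combined protocol and SAP*

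**What the plan says.** **The draw.** Section 6.1.4 provides for "blood gas analysis (using the IL GEM Premier Co-oximeter or local clinical lab) at 90 minutes", or at the end of treatment if dosing stops sooner. The algorithm in Section 6.1.3 is meant to "compute the iCO dose to achieve a COHb level of 7% (target 6-8%) at 90 min", so this sample coincides with the intended COHb peak.

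**Who is to stay blinded.** Section 6.3: "The study drug assignment will be blinded to the subject, clinical team, study coordinators, and other study staff". The exception is the administering respiratory therapist and physician.

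**How COHb is protected.**
- Section 6.1.4 has unblinded staff carry out CO monitoring, "concealed from the study coordinator and clinical team".
- Section 6.3 says the administering staff "will conceal the gas cylinders, CO delivery device, and measurements of COHb, SpCO, and ambient CO levels". It also keeps unblinded results apart from blinded ones.
- COHb data go to a limited-access database project (Sections 6.1.4 and 6.3), and COHb printouts go to the unblinded subject file (Section 8.5.2).
- Section 8.1.1 names one device: "COHb levels will be measured using the IL GEM Premier Co-oximeter at specified time points on Days 1 through 3".

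**What is wanted from the gas.** Section 8.5.2, for the pre-treatment sample: "The following values will be recorded from the ABG or VBG results", followed by pH, PCO2, PO2 and base excess or deficit. Table 5 lists the first three for the 90-minute gas. COHb and oxyhemoglobin are not listed as blood-gas values.

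**The concern.** The protocol treats COHb as the measurement that reveals the arm and restricts it at each point where study staff handle it. The 90-minute gas is the one on-treatment sample allowed to leave that channel, and it leaves when COHb is expected to be highest. No section says which fields the hospital laboratory may report, or to whom.

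The people who could see such a report matter to the outcomes. One pre-specified safety event is a rise in FiO2 of at least 0.2 together with a rise in PEEP of at least 5 cm H2O within 6 hours of dosing (Section 8.7.3). The documents do not say who makes those changes; I assume the treating team. PaO2/FiO2, OI, the PEEP part of LIS and ventilator-free days also depend on ventilator management. Under Section 8.7.5, blinded coordinators collect adverse events daily and a blinded physician evaluates changes in laboratory values. Under Section 8.7.4.2, that physician assesses relatedness.

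**Working it through.** The plan states no figure on this point, so there is none to reproduce. Three things can be checked.

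**1. Does any written safeguard reach a hospital-laboratory report?**

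| Safeguard | Section | What it controls |
|---|---|---|
| CO monitoring by unblinded staff, concealed | 6.1.4 | Measurements made by study staff |
| Limited-access database project | 6.1.4, 6.3 | Data entered by study staff |
| Printouts in unblinded file | 8.5.2 | Paper COHb results |
| Administering staff conceal COHb, SpCO and ambient CO | 6.3 | A general duty on those staff; no mechanism for a result the hospital issues |

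The principle is stated. The means of applying it to a hospital report is not.

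**2. If COHb were on that report, would it reveal the arm?**

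Inputs: Phase I placebo COHb 1.97 ± 0.39% (Section 2.2.5); target 6–8%, aim 7% (Section 6.1.3). Distance from placebo = (value − 1.97)/SD. The text does not say whether ± is an SD or a standard error. If it is a standard error with n=4, SD = 0.39 × √4 = 0.78.

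| COHb | SD 0.39 | SD 0.78 |
|---|---|---|
| 7% (aim) | 5.03/0.39 = 12.9 | 6.4 |
| 6% (lower target limit) | 4.03/0.39 = 10.3 | 5.2 |
| 4.9% (Phase I 200 ppm mean) | 2.93/0.39 = 7.5 | 3.8 |

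Under a normal model, the probability that a placebo value exceeds 4% is about 1 in 10 million with SD 0.39, and about 0.005 with SD 0.78. The documents give no COHb SD under algorithm dosing. The 0.6 in Section 9.2 is a planning SD for measured-minus-predicted COHb, so I do not use it here.

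Table 3 (healthy volunteers) shows which fields carry the information. The probability that one value from each arm is correctly ordered is AUC = Φ(|m1 − m0|/√(s0² + s1²)):
- COHb: 5.4/√(0.7² + 1.7²) = 2.94, AUC 0.998
- Oxyhemoglobin: 4.0/√(2.1² + 1.9²) = 1.41, AUC 0.92
- pH: 0.01/√(0.02² + 0.02²) = 0.35, AUC 0.64
- PaO2: 2.5/√(11² + 7.3²) = 0.19, AUC 0.58

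The fields the protocol wants and that Table 3 covers (pH, PaO2) say little about the arm. A co-oximetry field would give it away.

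Exposure: 36 × 3 = 108 possible treatments, of which 24 × 3 = 72 are iCO.

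**3. Do later gases carry the same information?**

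This uses CFK decay from 7% with the inputs printed under Table 4. Blood volume of 74 mL/kg and conventional values for the other constants are assumptions; with them the model reproduces Table 4's 7.0% at 400 ppm and 90 minutes.

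| FiO2 | 90 min after dosing | 180 min after dosing |
|---|---|---|
| 0.6 | 4.1% | 2.5% |
| 0.4 | 5.1% | 3.7% |

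At FiO2 0.6 and 180 minutes the distance is (2.5 − 1.97)/0.39 = 1.4 placebo SDs, or 0.7 with SD 0.78. That does not identify the arm. Later gases are informative only if drawn early or at lower FiO2.

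**The case against.** **The documents do not show an unblinding.** This stands. A reader might infer from Section 6.1.4 that the arm is posted to the medical record at each treatment. That needs two facts the documents do not give: that the site's panel reports COHb or oxyhemoglobin, and that the report reaches a chart blinded staff read. The protocol asks only for values that barely separate the arms. Site handling may also be covered in the SOP or Manual of Operations, which are not in these documents.

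**The principle is already written.** This stands in part. Section 6.3 requires COHb measurements to be concealed without limiting this to one device, and it makes inadvertent unblinding reportable to the DSMB. Neither provision keeps a hospital report away from the ICU team.

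**The effect on the primary endpoints is narrow.** This largely stands.
- The accuracy endpoint is a measured COHb.
- COHb ≥10% and the lactate rise are laboratory thresholds.
- MI and stroke have formal definitions with subspecialty consultation.
- Pre-specified events within their windows always count as suspected reactions, whoever reviews them, and the Medical Monitors already review unblinded (Section 8.7.4.2).
- Chest X-rays for LIS are read centrally by blinded investigators.
- A ventilator protocol limits bedside discretion.

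**Clinically ordered gases are a leak too.** A reader might extend the point to these gases and ask laboratories to mask their COHb. The decay figures do not support treating later gases as generally revealing. Masking them would also withhold results from the treating team.

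**Conclusion.** The point holds as an unaddressed, conditional blinding risk. Section 6.1.4 gives a route by which a sample at the intended COHb peak can bypass the protocol's COHb concealment, and no section closes it. If both site assumptions are true, a 90-minute COHb in or near the target range identifies the arm almost surely, whichever way the Phase I ± is read. If either is false, this route is closed at that site.

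The outcomes exposed are mainly the FiO2/PEEP hypoxemia event, attribution of adverse events that are not pre-specified, and secondary endpoints driven by ventilator settings. The accuracy endpoint and the laboratory-threshold events are little affected. The trial is openly only partially double-blind, but the people at issue are those Section 6.3 undertakes to keep blinded. The change is worth making because it costs almost nothing, not because bias has been shown.

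**What to change.** In Section 6.1.4, delete the local-laboratory alternative for the 90-minute or early-stop gas and state that:
- the gas is run by unblinded staff on the bedside IL GEM Premier;
- the full printout goes in the unblinded subject file;
- only pH, PCO2, PO2 and base excess are passed to blinded staff.

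The pre-treatment gas in Section 8.5.2 can stay as it is. Section 4.3 puts 4–6 half-lives between treatments. After four, the excess over the placebo mean is (7 − 1.97)/2⁴ = 0.31 percentage points, less than one placebo SD. No new unblinding report is needed, since Section 6.3 already provides one, and clinically ordered gases are left alone.

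**Cost:** a protocol wording change. The device and unblinded staff are already at the bedside, and Table 5 already schedules a 90-minute COHb on that device. One side effect is that, where the pre-treatment gas was run locally, the before-and-after comparison crosses two instruments. The current text already allows that mix.
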